### 9.2.2 Reversal Phase Protein Arrays (RPPA):

RPPA is a quantitative assay that analyzes nanolitre of sample for potentially hundreds of proteins (Iadevaia *et al.*, 2010). This antibody-based assay determines levels of protein expression, as well as protein modifications such as phosphorylation. RPPA allows concordant interrogation of multiple signaling molecules and their functional status. In essence, the RPPA study has major strengths in identification and validation of cellular targets, characterization of signaling pathways and networks, as well as determination of on and off target activity of drugs. We hypothesize that the integrated information derived from RPPA will display functional outcomes affected by MEK and/or AKT inhibition that will confirm target modulation and inform on predictors of response or mechanisms of resistance. As an exploratory endpoint each sample subjected to RPPA will be analyzed for effects on cell cycle, apoptosis, functional proteomics, and signaling network activity. The results across patients will be classified and compared with clinical responses to generate a “molecular signature” of functional outcomes affected by MEK and/or AKT inhibition.

In order to preserve the phospho-epitopes in samples that are shipped overnight and thus reduce the risk of false PD readouts, a BM pull will be immediately placed into a collection tube containing fix/lyse buffer. We have used this whole BM fixation and RBC lysis protocol for flow

cytometry applications (Chow *et al.*, 2008) and demonstrated that phospho-epitopes and CD surface markers are preserved and thus allows for CD138 selection of myeloma cells. The CD138 selected cells will then be snap frozen and serial samples batched for preparation of protein lysates using and shipping to the MD Anderson RPPA core facility. Their RPPA platform incorporates 130 validated antibodies that cover a wide spectrum of signaling molecules. A more detail description of sample preparation for RPPA is provided in the lab manual. The MD Anderson RPPA facility has extensively validated antibodies suitable for RPPA however the feasibility of the protein extraction for RPPA application is yet to be determined.

The products of these correlative studies are to validate and identify novel biomarkers related to MM responses and outcomes to MEK inhibitors that may then enter into development as clinical assays. In addition, we expect to begin testing hypotheses around novel biomarkers and mechanisms of resistance that may inform combination strategies and guide the development of innovative, personalized therapeutics for MM and cancers and general.

### **9.3 RAS and BRAF mutation detection using circulating free DNA (cfDNA)**

As a pilot study within this protocol, the feasibility of deriving cfDNA from patients for detection of mutations of RAS and BRAF will be assessed. Currently, the detection of RAS and BRAF mutations is carried out in tumor tissue by next generation sequencing. This requires bone marrow aspiration for derivation of tumor tissue and CD138 purification of myeloma tumor cells for DNA extraction. Recent studies have validated the detection of KRAS and BRAF mutations from circulating free tumor DNA (cfDNA). cfDNA was detected in 100% of patients with metastatic colorectal cancer and showed 100% specificity and sensitivity for BRAFV600E mutation and 98% specificity and 92% sensitivity for KRAS mutations (*Thierry AR et al. 2014*). Thus, this represents a minimally invasive and cost-effective method for identification of patients that are most likely to benefit from targeted therapy.

For patients that are biomarker positive peripheral blood will be collected at all applicable time points and will be processed as per the Study Lab Manual. cfDNA will be extracted using the QIAamp DNA MINI Blood kit (Qiagen) according to the manufacturer's protocol. The DNA will be used to perform ultra-deep sequencing of KRAS, NRAS and BRAF using a two-step PCR-based approach, TAM-Seq followed by Illumina sequencing.

Our goals are first to determine our ability to derive cfDNA at multiple time points. To compare the sensitivity and specificity of RAS and RAF mutational analysis of peripheral blood cfDNA compared to detection using standard methods from tumor specimens. To determine whether mutational load over the treatment course can be evaluated from cfDNA. It is hoped that this will lead to the development of a less invasive and more efficient platform for the identification of MM patients that may benefit from targeted therapies.

### **9.4 Laboratory Correlative Studies**

Please see lab manual for Correlative studies collection, shipping, and process instructions.

## 10 STUDY CALENDAR

Baseline evaluations are to be conducted within 1 week prior to start of protocol therapy, unless specified differently in the study calendar. Scans and x-rays, ECHO/MUGA, and Ophthalmology exam must be done  $\leq 4$  weeks prior to the start of therapy. In the event that the patient's condition is deteriorating, laboratory evaluations should be repeated within 48 hours prior to initiation of the next cycle of therapy. If pre-study assessments were done within 3 days of treatment initiation, they do not need to be repeated for cycle 1 day 1. For subsequent cycles (2+), day 1 assessments can be completed up to 48 hrs prior to day 1. All day 15 assessments can be completed up to 48 hrs prior to day 15. Baseline myeloma disease assessment can be done  $\leq 4$  weeks prior to the start of therapy (see [11.2.1](#)). Response assessment can be done up to  $\leq 7$  days prior to the start of the next cycle to allow for treatment decisions to be made with regards to the addition of GSK2141795 for stable disease or progression prior the initiation of the next cycle.

PROCEDURES	Screen	Cycle 1-2 Single Agent (cycle=28 days)		Cycles 3+ Single Agent	Cycle 1-2 Combination		Cycles 3+ Combination	Off Study	Safety Follow-up
		Day1	Day15	At the start of every Cycle	Day1	Day 15	At the start of every cycle		
Trametinib		A-----A			A*-----A*				4 weeks (+ 3 days) after last treatment
GSK2141795					B-----B				
Informed consent	X								
Demographics	X								
Medical history	X								
Concurrent meds	X	X-----X						X	
Physical exam	X	X		X	X		X	X	
Vital signs	X	X	X	X	X	X	X	X	
Height	X								
Weight	X	X	X	X	X	X	X	X	
Performance status	X	X	X	X	X	X	X	X	
CBC w/diff, plts	X	X	X	X	X	X	X	X	
Fasting serum chemistry a	X	X	X	X	X	X	X	X	
TSH	X				X		X i	X	
Serum viscosity m	X								
ECG b	X	X	X	X		X		X	
Echocardiogram or MUGA	X	Every 12 weeks (use same methodology for baseline and follow up).							
Ophthalmology exam l	X	as clinically indicated k							
Visual acuity exam k	X	X		X	X		X	X	
Adverse event evaluation		X-----X						X	X i
Myeloma disease assessment c (section 11.2.1)	X	Assessments are repeated every 4 weeks. Documentation must be provided for patients removed from study for progressive disease.						X	

Radiologic evaluation d	X	Radiologic measurements, if indicated, for assessment of extramedullary disease should be performed every 12 weeks or upon clinical suspicion of progressive disease.						X	
B-HCG c	X	X						X	
Glycosylated Hemoglobin (HbA1c)	X				X				
PT/INR & PTT	X	X			X				
Urinalysis	X	X	X	X	X	X	X	X	
Skeletal Survey e	X								
Survival Follow-up									X
Correlative studiesh: Peripheral blood and BM aspirate	X	On Day -2 to 1 of Cycle 2, 2-4 h after dosing with trametinib AND at progression And peripheral blood sample every even cycle for biomarker positive patients only			On Day -2 to 1 of Cycle 2, 2-4 h after dosing with trametinib and GSK2141795 AND at progression And peripheral blood sample every even cycle for biomarker positive patients only				

A. [Trametinib]: 2 mg daily of a 28 day cycle  A* Trametinib 1.5 mg daily of a 28 day cycle (when used in combination with GSK2141795)
 
B. [GSK2141795]: 50 mg daily of a 28 day cycle
 
a. Albumin, alkaline phosphatase, total bilirubin, bicarbonate, BUN, calcium, chloride, creatinine, LDH, magnesium, phosphorus, potassium, total protein, SGOT [AST], SGPT [ALT], sodium, fasting serum glucose. Weight and serum creatinine will be used to calculate creatinine clearance (eGFR and eCCR). Also see protocol guidelines for patient management and reporting of elevated liver function tests.
 
b. A single 12-lead ECG should be performed at screening and on the indicated visits. The QT interval corrected for heart rate should be calculated using the Bazett's formula. (<math>QT_c = QT / \sqrt{RR}</math>)
 
c. Myeloma lab tests: <math>\beta</math>2Microglobulin (collected at screening only); serum immunoelectrophoresis, immunoglobulin assay, M band confirmation by immunofixation and quantitation by SPEP, free light chain and 24 hour urine collection for Bence Jones protein to be performed at baseline prior to study, prior to each cycle thereafter and at time of study discontinuation (if last tests were > 4 weeks). FreeLyte test should occur if indicated by the Investigator. Not all tests may be required at each assessment time point. Tests can be done up to 7 days prior to day 1 of each cycle.
 
d. Radiological assessment for clinically suspected extramedullary disease should be performed prior to study (28 days) and every 12 weeks or upon clinical suspicion of progressive disease. This may include CT scan of the abdomen/pelvis, CT or x-ray of the chest, or ultrasound of the liver/spleen or abdomen. To ensure comparability, the baseline radiographs/scans and subsequent radiographs/scans to assess response should be performed preferably using identical techniques. The same method, radiological or physical, should be employed and assessed by the same individual on each occasion if possible.
 
e. Serum pregnancy test (women of childbearing potential).
 
g. Skeletal survey (including skull, all long bones, pelvis and chest) required if previous survey >12 weeks from study entry and at any time when clinically indicated.
 
h. Details on collection of samples, handling and shipping are provided in the Study Lab Manual. The patient may be dosed prior to study visit on cycle 2 day 1 (of single agent trametinib) and cycle 2 day 1 (of combination) to facilitate 2-4 h waiting for bone marrow aspiration. Baseline correlatives can be > 4 weeks prior to start of protocol therapy providing collection is after informed consent.
 
i. Refer to section 5.4
 
j. TSH testing to be done at the beginning of every 4th cycle
 
k. Snellen Chart and Visual Field Testing. If results of visual testing are abnormal the patient will be referred for an urgent full ophthalmologic exam
 
l. The exam will include indirect fundoscopic examination, visual acuity (corrected), visual field examination, tonometry, and direct funduscopy.
 
m. To be performed if available at the treating institution.
									

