#### Antitumor Activity of Trametinib in Cancer Other Than Melanoma

In a phase 1/2 monotherapy study, acute myeloid leukemia (AML) or myelodysplastic syndrome (MDS) patients were given trametinib at dose levels from 1-2 mg QD. Drug-related AEs in 45 patients were similar to that observed in patients with solid tumors, and 2 mg PO QD was selected for further investigation in this patient population. Twelve patients (23%) withdrew due to an AE, including cardiac failure (2) and infection (2). Efficacy was reported in 39 patients (Borthakur *et al.*, 2010). The best response in 13 patients with KRAS or NRAS mutations included 3 CRs (23%), 7 SD (54%), and 1 PD (progressive disease) (5%). In 26 patients with wild-type RAS or an unknown mutation, there were 2 PRs (8%).

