Cardiac-related AEs: At the 2 mg monotherapy dose, 3% to 21% of the subjects in six studies had cardiac-related AEs (Investigator's Brochure, 2013). Of the 65 total subjects (including crossover subjects) experiencing cardiac-related AEs at the 2.0 mg monotherapy dose in five of the studies, the majority of cardiac-related AEs were grades 1 or 2 in severity (0% to 16% of all study subjects); 18 subjects had grade 3 cardiac-related AEs, and no subjects had Grade 4 cardiac-related AEs in any study. No subject in one study, which evaluated the effect of repeat oral dosing of trametinib 2 mg QD on cardiac repolarization in subjects with solid tumors, had cardiac-related AEs. One study subject receiving trametinib 2 mg QD had grade 5 (fatal) acute cardiac failure, with evidence of massive tumor invasion of the heart; this AE was considered not drug-related by the investigator.

In the phase 3 trial of trametinib vs. chemotherapy in patients with melanoma (MEK114267), cardiomyopathy (defined as cardiac failure, left ventricular dysfunction, or decreased LVEF) occurred in 7% (14/211) of patients treated with trametinib, and in no patients in the chemotherapy arm. Cardiomyopathy was identified within the first month of treatment in five of these 14 patients; median onset of cardiomyopathy was 63 days (range: 16 to 156 days). Cardiomyopathy resolved in 10 of these 14 (71%) patients. Cardiac monitoring should be included in trametinib protocols, to include LVEF assessment by echocardiogram or MUGA scan at baseline, one month after initiation of trametinib and then at 2- to 3-month intervals while on treatment. Refer to dose modification guidelines for cardiac AEs in the event of LVEF decline or symptomatic cardiac AEs.

Pneumonitis: At the 2 mg monotherapy dose, 0% to 4% of the subjects in five studies had pneumonitis (Investigator's Brochure, 2013). Of the nine total subjects (including crossovers) experiencing pneumonitis AEs at this dose, three subjects had grade 1 or 2 pneumonitis and six subjects had grade 3 pneumonitis.

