Embryofetal toxicity: Based on its mechanism of action, trametinib can cause fetal harm when administered to a pregnant woman. Trametinib was embryotoxic and abortifacient in rabbits at doses greater than or equal to those resulting in exposures approximately 0.3 times the human exposure at the recommended clinical dose. If this drug is used during pregnancy, or if the patient becomes pregnant while taking this drug, the patient should be apprised of the potential hazard to a fetus.

*Incidence of common AEs reported from a phase III trial of trametinib vs. chemotherapy in patients with advanced melanoma:*

Patients with abnormal LVEF, history of acute coronary syndrome within 6 months, or current evidence of Class II or greater congestive heart failure (New York Heart Association) were excluded from this trial. Selected adverse reactions (AR) occurring in patients receiving

trametinib as compared to patients in the chemotherapy arm are listed as below:

**Table:** Selected adverse reactions (ARs) occurring in  $\geq 10\%$  of patients receiving trametinib AND at a higher incidence than in the chemotherapy arm (high in the trametinib arm compared with chemotherapy by  $\geq 5\%$  in overall incidence or by  $\geq 2\%$  grade 3 or 4 AEs)

Adverse Reactions	Trametinib (n=211)		Chemotherapy (n=99)	
	All Grades	Grades 3 and 4	All Grades	Grades 3 and 4
Skin and subcutaneous tissue disorders				
Rash	57	8	10	0
Dermatitis acneiform	19	<1	1	0
Dry skin	11	0	0	0
Pruritis	10	2	1	0
Paronychia	10	0	1	0
Gastrointestinal disorders				
Diarrhea	43	0	16	2
Stomatitis	15	2	2	0
Abdominal pain	13	1	5	1
Vascular disorders				
Lymphedema	32	1	4	0
Hypertension	15	12	7	3
Hemorrhage	13	<1	0	0

**Table:** Percent-patient incidence of laboratory abnormalities occurring at a higher incidence in patients treated with trametinib versus chemotherapy (between-arm difference of  $\geq 5\%$  [all grades] or  $\geq 2\%$  [grades 3 or 4])

Preferred term	Trametinib (n=211)		Chemotherapy (n=99)	
	All Grades	Grades 3 and 4	All Grades	Grades 3 and 4
Increased aspartate aminotransferase (AST)	60	2	16	1
Increased alanine aminotransferase (ALT)	39	3	20	3
Hypoalbuminemia	42	2	23	1
Anemia	38	2	26	3
Increased alkaline phosphatase	24	2	18	3

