- 3.2.9 *In vitro* data indicate that GSK2141795 is a CYP3A4 substrate. Drugs that potently inhibit CYP3A4 could lead to increased GSK2141795 exposure in subjects, and should either be prohibited or used with caution. Drugs which are strong inducers of CYP3A4 and may result in lower exposures of GSK2141795 should also be prohibited. GSK2141795 also appears to be a moderate *in vitro* inhibitor of CYP2C8 (50% inhibitory concentration [IC50] 3 mcM) and CYP3A4 (IC50 11 mcM). Drugs that are substrates of CYP3A4 or CYP2C8 with a narrow therapeutic index may be prohibited. Drugs that are sensitive substrates of CYP3A4 or CYP2C8 should be used with caution. (Refer to 5.2.3)
- 3.2.10 History or current evidence/risk of retinal vein occlusion (RVO) or Retinal Pigment Epithelial Detachment (RPED):
- History of RVO or RPED, or predisposing factors to RVO or RPED (*e.g.*, uncontrolled glaucoma or ocular hypertension, uncontrolled systemic disease such as hypertension, diabetes mellitus, or history of hyperviscosity or hypercoagulability syndromes).
  - Visible retinal pathology as assessed by ophthalmic exam that is considered a risk factor for RVO or RPED such as evidence of new optic disc cupping, evidence of new visual field defects, and intraocular pressure >21 mm Hg.

3.2.11 History or evidence of cardiovascular risk including any of the following:

- LVEF < LLN.
- A QT interval corrected for heart rate using the Bazett's formula  $QTcB \geq 480$  msec ( $\geq 500$  msec for subjects with bundle branch block)
- History or evidence of current clinically significant uncontrolled arrhythmias (exception: patients with controlled atrial fibrillation for >30 days prior to randomization are eligible).
- Other clinically significant ECG abnormalities including 2nd degree (Type II) or 3rd degree atrioventricular (AV) block.
- Subject with intra-cardiac defibrillators or pacemakers.
- History of acute coronary syndromes (including myocardial infarction and unstable angina), coronary angioplasty, or stenting within 6 months prior to randomization.
- History or evidence of current  $\geq$  Class II congestive heart failure as defined by the New York Heart Association (NYHA) functional classification system
- Treatment-refractory hypertension defined as a blood pressure of systolic >140 mmHg and/or diastolic >90 mmHg which cannot be controlled by anti-hypertensive therapy.
- Known cardiac metastases.

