### 6.1.7 Trametinib Dose Modification for Reduced Left Ventricular Ejection Fraction

Decreases of the left ventricular ejection fraction (LVEF) have been observed in patients receiving trametinib. Therefore, ECHOs must be performed in regular intervals outlined in the Study Calendar. The same procedure (either ECHO or MUGA, although ECHO is preferred) should be performed at baseline and at follow-up visit(s).

Trametinib Dose Modification Guidelines and Stopping Criteria for LVEF Decrease		
Clinic	LVEF-drop (%) or CTCAE grade	Action and Dose Modification
Asymptomatic	Absolute decrease of >10% in LVEF compared to baseline and ejection fraction below the institution's LLN.	
 
• Interrupt trametinib and repeat ECHO/MUGA within 2 weeks.a
 
• If the LVEF recovers within 4 weeks (defined as LVEF ≥ LLN and absolute decrease ≤ 10% compared to baseline):               
 
– Consult with the CTEP trametinib medical monitor and request approval for restart.
 
– Restart treatment with trametinib at reduced dose by one dose level.b
 
– Repeat ECHO/MUGA 2, 4, 8, and 12 weeks after re-start; continue in intervals of 12 weeks thereafter.
 
 
 
• If LVEF does not recover within 4 weeks:               
 
– Consult with cardiologist.
 
– Permanently discontinue trametinib.
 
– Report as SAE
 
– Repeat ECHO/MUGA after 2, 4, 8, 12, and 16 weeks or until resolution.
 
– Consult with the CTEP trametinib medical monitor.c
 
 
 

Symptomaticb	
 
• Grade 3: resting LVEF 39-20% or >20% absolute reduction from baseline
 
• Grade 4: Resting LVEF ≤ 20%.
 
	
 
• Permanently discontinue trametinib.
 
• Report as SAE.
 
• Consult with cardiologist.
 
• Repeat ECHO/MUGA after 2, 4, 8, 12, and 16 weeks or until resolution.
 

a If ECHO/MUGA does not show LVEF recovery after 2 weeks, repeat ECHO/MUGA 2 weeks later.  
b Escalation of trametinib to previous dose level can be considered if LVEF remains stable for 4 weeks after restarting of trametinib. Approval from the CTEP trametinib medical monitor is required.  

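### The platelet hold for grade 3 with bleeding (6.1.13) can be released while the bleeding continues, and the Study Calendar omits the one-month LVEF test that 2.2.1.3 calls for

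*Combined protocol and SAP*

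**What the plan says.** **Platelets.** The table in section 6.1.13 holds drug in two situations: grade 3 thrombocytopenia (below 50,000/ul) accompanied by bleeding of grade 2 or worse, and grade 4 (below 25,000/ul). A single release rule serves both, namely recovery of the count to 30,000/ul. Bleeding is part of the trigger but not of the release. A footnote takes patients off protocol therapy if the delay reaches 28 days.

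**LVEF.** Section 2.2.1.3 says trametinib protocols should assess LVEF at baseline, "one month after initiation of trametinib and then at 2- to 3-month intervals while on treatment". Section 6.1.7 leaves the timing to the calendar: "ECHOs must be performed in regular intervals outlined in the Study Calendar". The Study Calendar (section 10) has ECHO/MUGA at screening and then "Every 12 weeks (use same methodology for baseline and follow up". No calendar footnote adds a one-month test. The repeat scans listed in 6.1.7 apply only after a fall has been measured.

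**The concern.** **Platelets.** Drug is stopped because the patient has a low count and is bleeding. If the count is already above the release level, the table's own rule ends the hold at once, and it does not say which instruction governs. Entry is allowed at 50 x 10^9/L (3.1.10), so a small fall reaches grade 3. The trametinib risk list in 7.1.1.1 includes hemorrhage, with fatal intracranial cases.

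**LVEF.** The asymptomatic rule in 6.1.7 requires "Absolute decrease of >10% in LVEF compared to baseline" together with a value below the institution's lower limit of normal. Only ECHO or MUGA can show this; the scheduled examinations, vital signs and ECGs do not measure LVEF. Until the first scheduled scan, the rule has nothing to act on. Section 6.1 also allows GSK2141795 to be added for progression after 2 cycles (2 x 28 = 56 days), so a patient could start the combination without an on-treatment LVEF.

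**Working it through.** **1. Platelet trigger against platelet release**

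| Count (/ul), with grade 2 or worse bleeding | Hold starts? | Release level met at that moment? |
|---|---|---|
| 30,000 to 49,999 | yes (grade 3) | yes |
| 25,000 to 29,999 | yes (grade 3) | no |
| below 25,000 | yes (grade 4) | no |

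The release threshold does some work only in the lowest part of the grade 3 range. The overlap is (50,000 - 30,000) / (50,000 - 25,000) = 20,000 / 25,000 = 80% of the width of that range. This is a share of a laboratory interval, not of patients. The protocol gives no distribution of counts or bleeds, so no patient frequency follows.

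Other text gives partial cover. The table in 6.1.1 interrupts drug for related grade 2 or grade 3 toxicity until grade 1 or baseline, and permanently stops it at grade 4. Bleeding is not among the events that table excludes, so a bleed judged drug-related stays on hold under 6.1.1 whatever the count. The trigger in 6.1.13 does not ask about attribution. What remains is a bleed judged unrelated: it starts the hold in 6.1.13, but neither section ties the restart to its resolution.

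**2. First scheduled on-treatment LVEF**

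The calendar does not say where the 12 weeks start, and the screening ECHO/MUGA may be done up to 4 weeks before therapy.

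- Counted from first dose: 12 x 7 = day 84.
- Counted from a screening scan at day -28: -28 + 84 = day 56.
- One month as 2.2.1.3 asks: about day 28.

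The 12-week spacing fits the later interval of 2 to 3 months. Only the one-month test is missing.

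**3. Size of the early risk, from the trial cited in 2.2.1.3**

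The stated overall incidence reproduces: 14/211 = 6.6%, given as 7%. On timing, "Cardiomyopathy was identified within the first month of treatment in five of these 14 patients"; median onset was 63 days (range 16 to 156). With 14 cases and a median of 63 days, at least 7 arose by day 63, which is before day 84 though not necessarily before day 56.

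- Month-1 rate: p = 5/211 = 2.37%, exact (Clopper-Pearson) 95% CI 0.77 to 5.44%.
- Expected month-1 cases = N x p; chance of at least one = 1 - (1 - p)^N.

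| N | Expected cases (range over CI) | Chance of at least one (range over CI) |
|---|---|---|
| 24 (minimum, 13.2) | 0.57 (0.19 to 1.31) | 44% (17 to 74%) |
| 74 (both groups reach stage two) | 1.75 (0.57 to 4.03) | 83% (44 to 98%) |

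These figures assume that the melanoma rate carries over to myeloma. They count every month-1 case, however it was found.

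**4. Scans added by a week-4 start**

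For a patient treated for T weeks (T at least 4), scans at weeks 4, 16, 28 number floor((T - 4)/12) + 1. Scans at weeks 12, 24, 36 number floor(T/12). The difference is 1 for T from 4 to under 12 and from 16 to under 24, and 0 for T from 12 to under 16 and from 24 to under 28; the pattern then repeats. It never exceeds one.

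**The case against.** **Platelets.** The strongest reply is that bleeding is already managed elsewhere. Section 6.1.1 covers related bleeds, and because hemorrhage is a listed trametinib event, many bleeds would be attributed at least as possible. Section 5.3 lets the investigator stop treatment for intercurrent illness or a change in condition. Most of this stands and narrows the gap. But 5.3 lists reasons to end treatment, not a rule for holding and restarting, and 6.1.13 does not refer to either section. A reader might infer that the protocol generally lets bleeding patients resume drug, or that 80% of affected patients are exposed. The documents support neither.

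**LVEF.** It can be said that 2.2.1.3 is background text and that the calendar is what sites follow. That is true, but the background states what a trametinib protocol should contain, and no operative section gives a reason for departing from it.

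Several stronger readings are tempting:

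- *That the first scan is fixed at day 84.* The starting point of the 12 weeks is not stated, so only a range can be given.
- *That 83% is the chance a week-4 scan finds a case.* It needs all 74 patients, and 2.2.1.3 does not say whether the five early cases were found by scan or by symptoms.
- *That the two trials' cardiac exclusions are the same.* The melanoma trial excluded "Patients with abnormal LVEF, history of acute coronary syndrome within 6 months, or current evidence of Class II or greater congestive heart failure". Section 3.2.11 covers these and goes further, for example "History of acute coronary syndromes (including myocardial infarction and unstable angina), coronary angioplasty, or stenting within 6 months prior to randomization", and adds QTc limits, pacemakers and refractory hypertension. On the text available this trial's list is broader, so the transfer of 5/211 is less secure.
- *That the AML/MDS withdrawals for cardiac failure support early scanning.* Their timing is not given.
- *That the footnote in 6.1.11 on more than two reductions permits a second GSK2141795 reduction.* Section 6.1 already caps that drug at one.

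**Conclusion.** Both points hold in a limited form.

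The release rule in 6.1.13 is wrong as written. For grade 3 counts of 30,000/ul or more it is satisfied at the moment the hold begins, while the patient is bleeding. After allowing for 6.1.1, the practical gap is bleeds judged unrelated to study drug, of unknown frequency.

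The LVEF point is a mismatch between the protocol's own safety text and its calendar: one test is missing, and the first scheduled on-treatment measurement comes at about day 56 to 84 instead of about day 28. If the melanoma month-1 rate applies, about 0.6 cases in 24 patients or 1.8 in 74 would be expected in that month, as upper limits on what a week-4 scan would detect.

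These are matters of patient management. The response endpoint, the error rates and the sample size are untouched.

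**What to change.** **6.1.13.** For grade 3 with grade 2 or worse bleeding, write that drug is held until bleeding is grade 1 or less and platelets are at least 30,000/ul. Leave the grade 4 rule as it is. The cost is slightly longer holds for some patients, a few of whom could reach the 28-day limit and leave protocol therapy.

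**Study Calendar.** Set the first on-treatment ECHO/MUGA at week 4 (start of cycle 2) and count the 12-week interval from there: weeks 4, 16, 28 and so on. This meets 2.2.1.3, removes the doubt about where the interval starts, and adds at most one scan for some patients and none for others. The trade-off is that, compared with counting from first dose, the next scan moves from week 12 to week 16, so a fall arising between weeks 4 and 12 would be seen later; the cited median onset of 63 days lies in that window. Keeping weeks 12, 24 and so on in addition to week 4 avoids this, at the price of one extra scan for every patient still on treatment at week 4 (at most 24 to 74 scans in all).
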